## EXPERIMENTAL CLINICAL PROTOCOL

**TITLE OF THE STUDY:** “Cerebello-Spinal tDCS as Rehabilitative Intervention in Neurodegenerative Ataxia”

**ACRONYM:** SCA02

**VERSION AND DATE:** Version 2 of September 4, 2018

**DIVISION WHERE THE RESEARCH IS PERFORMED:** Clinica Neurologica, Università di Brescia, Spedali Civili di Brescia

**MAIN EXPERIMENTATOR:** [name]

**INTRODUCTION AND RATIONAL:** Transcranial stimulation with direct currents or transcranial direct current stimulation, tDCS is a neurophysiological method of non-invasive modulation of the central nervous system excitability, which is having an increasing diffusion and an increasingly numerous spectrum of potentials therapeutic applications such as, for example, post-stroke rehabilitation, depression and pain, already consolidated. This method, being non-invasive, low-cost and simple to carry out, has the potential to be widely used both as a research tool and as a support tool for rehabilitation treatment, as in the case of Spinocerebellar Ataxias, a group of neurodegenerative pathologies based on genetics, characterized by slowly progressive ataxia of walking, posture and limbs, associated with dysarthria and / or alteration of oculomotion, for which no treatments are currently available. This method also finds application in Cerebellar Ataxias of neurodegenerative origin, such as in Multisystem Atrophy (MSA), in Friedreich Ataxia and in other Central Nervous System pathologies with selective involvement of cerebellar structures. Indeed, a positive effect of tDCS has been demonstrated in modulating cerebellar excitability in humans (Galea 2009) with a favorable effect of cerebellar anodic stimulation by tDCS on motor learning and walking (Jayaram 2012). Based on these premises, the treatment of patients with Cerebellar Ataxias of neurodegenerative origin is proposed (for example SCA, MSA, Friedreich's Ataxia).

Transcranial magnetic stimulation (TMS) techniques have been widely used in the study of neurodegenerative diseases, particularly in Parkinson's disease and dementia due to Alzheimer's disease. Over the years, numerous transcranial magnetic stimulation protocols have been developed to obtain information on neurophysiological parameters

with the aim of investigating both the pathogenesis and the evolution of some neurodegenerative pathologies.

The study of the cerebellar-brain inhibition (CBI) allows us to investigate the physiological inhibitory activity of the cerebellar cortex on motor circuits. This stimulation protocol is evaluated through the simultaneous magnetic stimulation of the cerebellar cortex and of the motor cortex with two separate coils (Carrillo 2014; Koch 2014). Some studies have in fact highlighted an alteration of cerebello-motor connectivity, assessed by CBI protocol, in patients suffering from cerebellar ataxias of degenerative origin (Ugawa 1994; Ugawa 1997; Conde 2013; Bonni 2014).

**OBJECTIVES:** The aim of the study is to evaluate the long-term effects on cognitive performance, quality of life and motor performance, in particular coordination and balance, of tDCS applied at the level of the cerebellar cortex and at the spinal level in patients suffering from cerebellar ataxias of degenerative origin to identify a possible rehabilitation protocol. The effect of tDCS on cerebello-motor connectivity will also be evaluated by CBI TMS protocol.

**PROCEDURES:** Patients already enrolled at the Neurological Clinic recognized as suffering from cerebellar ataxia of degenerative origin according to the current clinical criteria will be enrolled, with a disorder of motor coordination, walking or a mild to moderate balance, which are due to regular clinical controls. Patients will be divided into two groups. The first group will undergo stimulation protocol by means of tDCS, while the second group will be subjected to placebo (sham) treatment. Each session will consist of the application of ten sessions of tDCS at 2mA, at the level of the cerebellar cortex and at the spinal level (2 cm caudally at T11) for the duration of 20 min each. The effects will be evaluated before stimulation with tDCS, two weeks after treatment and three months. In particular, the effects on cognitive performance, quality of life and performance of motor coordination and balance will be evaluated by using dedicated scales. Finally, the effects on neurophysiological parameters of CBI will be evaluated by TMS.

**INCLUSION / EXCLUSION CRITERIA:** Patients with spino-cerebellar ataxia, Friedreich's ataxia, multisystem atrophy, sporadic ataxia in adult onset will be included. Patients affected by: i) cerebrovascular diseases, hydrocephalus, expansive intracranial processes ii) significant medical problems (eg diabetes and arterial hypertension poorly controlled; cancer in the past 5 years) will be excluded iii) major depressive disorders, bipolar disorders, schizophrenia, abuse of substances, mental retardation according to DSM-IV criteria) implanted metal objects or history of epilepsy. Patients should not suspend any ongoing therapy.

Presidio Ospedaliero  
di Brescia

Regione  
Lombardia  
ASST Spedali Civili

Università  
degli Studi  
di Brescia

CLINICA NEUROLOGICA - UNIVERSITA' DEGLI STUDI DI BRESCIA  
UO Neurologia 2 - AZIENDA SOCIO SANITARIA TERRITORIALE degli SPEDALI CIVILI DI BRESCIA  
Direttore: [name]

**STUDY DESIGN:** this is a randomized, double-blind, non-pharmacologic, placebo-controlled clinical trial, since neither patients nor those who will administer the evaluation tests will be aware of the type of treatment carried out, real-tDCS or sham (anodic tDCS: placebo tDCS = 1: 1) with cerebellar tDCS 5 days a week for 2 consecutive weeks in 40 patients with neurodegenerative ataxia.

A randomized stratification by type of pathology will be implemented, so as to balance the patients with the same pathology between the two groups (real and sham). Subsequently, a randomization in blocks will be implemented, in order to balance the quantitative asymmetry of the patients assigned to the two groups, guaranteeing a similar number of patients enrolled in the two groups, even if the trial should be interrupted early.

Patients with spinocerebellar ataxia, Friedreich's ataxia, multisystem atrophy, sporadic ataxia in adult onset will be included. Each patient will undergo a clinical evaluation (cognitive performance, quality of life and performance of motor coordination and balance), evaluation of CBI connectivity by transcranial magnetic stimulation at baseline (T0), after 2 weeks of treatment with tDCS (T1) and follow -up to 3 months (T2).

An open phase will follow and all patients will receive an anodic tDCS stimulation at the cerebellar and cathodic levels at the spinal level (5 days / week for 2 weeks) and will receive the same standardized evaluation after the 2-week treatment (T3), at the follow- up to 3 months (T4) and 6-month follow-up (T5).

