## **END POINTS:**

### ***Primary Outcome Measures:***

1. Change in the International Cooperative Ataxia Rating Scale (ICARS) Score (Baseline – 2 Weeks).
2. Change in the Scale for the Assessment and Rating of Ataxia (SARA) Score (Baseline – 2 Weeks).
3. Change in the Cerebellar cognitive affective syndrome (CCAS) Scale (Baseline – 2 Weeks).

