### ***Secondary Outcome Measures:***

4. Change in the International Cooperative Ataxia Rating Scale (ICARS) Score (Baseline - 2 weeks - 3 month - 6 months - 9 months).
5. Change in the Scale for the Assessment and Rating of Ataxia (SARA) Score (Baseline - 2 weeks - 3 month - 6 months - 9 months).
6. Change in the Cerebellar cognitive affective syndrome (CCAS) Scale (Baseline - 2 weeks - 3 month - 6 months - 9 months).

7. Change in Cerebellar Brain Inhibition (CBI) Measurements (Baseline - 2 weeks - 3 month - 6 months - 9 months).
8. Change in the Short-Form Health Survey 36 (SF36) Score (Baseline - 2 weeks - 3 month - 6 months - 9 months).

**STATISTICAL PLAN:** we will use parametric analyzes (t tests) to compare the demographic variables (age and education) of the two groups at the baseline. A  $P < 0.05$  will be considered significant. To evaluate the effect of the stimulation protocol by means of tDCS on cognitive performances, of motor coordination and balance and quality of life, at T 2-3-4-5 we will use a mixed-model ANOVA.

We performed a "power analysis" to estimate the sample size, based on some previously published studies (Benussi A, Brain Stimul, 2017) using methods similar to those applied in the study in question. The "effect size"  $f(V)$  was calculated by direct method. Taking into account the aforementioned studies an effect size equal to a partial  $\eta^2$  of 0.037, equal to an "effect size"  $f(V)$  of 0.195 and, considering alpha = 0.05 and the power  $(1-\beta) = 0.80$ , the expected sample size is 54 subjects using a repeated measures ANOVA study. The proposed sample size of 60 subjects should be adequate to achieve the main objective of the study.

**ETHICAL CONSIDERATIONS (RISK-BENEFIT):** tDCS is a non-invasive, low-cost and easy-to-implement method which is having an increasing diffusion and an increasingly numerous spectrum of potential therapeutic applications such as, for example, post-stroke rehabilitation, depression and pain, already consolidated. Recently its efficacy in modulating cerebellar excitability in humans (Galea 2009) has been demonstrated with favorable effect of cerebellar anodic stimulation by tDCS on motor learning and walking (Jayaram 2012).

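### The stated aim is long-term benefit, but every primary endpoint stops at 2 weeks, and the analysis plan does not isolate the one later sham-controlled comparison (T0 to T2)

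*Combined protocol and SAP*

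**What the plan says.** All references are to the combined protocol and SAP.

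- **Objectives.** "The aim of the study is to evaluate the long-term effects on cognitive performance, quality of life and motor performance", with a view to identifying a rehabilitation protocol. Long-term is not defined.
- **End Points, primary.** Three outcomes, all with the same window: "Change in the International Cooperative Ataxia Rating Scale (ICARS) Score (Baseline – 2 Weeks"), "Change in the Scale for the Assessment and Rating of Ataxia (SARA) Score (Baseline – 2 Weeks") and "Change in the Cerebellar cognitive affective syndrome (CCAS) Scale (Baseline – 2 Weeks").
- **End Points, secondary.** The same three scales, plus CBI and SF36, followed to 9 months, for example "Change in the Short-Form Health Survey 36 (SF36) Score (Baseline - 2 weeks - 3 month - 6 months - 9 months"). Quality of life appears only here.
- **Study Design.** In the randomized phase patients are assessed at baseline (T0), "after 2 weeks of treatment with tDCS (T1) and follow -up to 3 months (T2"). Then: "An open phase will follow and all patients will receive an anodic tDCS stimulation at the cerebellar and cathodic levels at the spinal level". T3, T4 and T5 belong to that open phase.
- **Statistical Plan.** The effect on cognition, coordination and balance, and quality of life is to be assessed by mixed-model ANOVA. The visits named are T2, T3, T4 and T5; T1 is not named. The power statement gives 54 subjects as required and 60 as proposed, and ties neither to an endpoint or visit.
- **Procedures.** The first post-treatment assessment is placed a fortnight following treatment, whereas Study Design places it at the close of the two-week course.

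**The concern.** The aim, the primary endpoints and the named analysis point to different times. The aim asks whether benefit lasts. The primary endpoints ask whether there is benefit at the first visit after treatment. The analysis sentence covers 3 months onward, most of it after the sham arm has crossed to real stimulation.

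The conclusion is what is at stake. An effect that has vanished by 3 months and one that is fully retained produce the same primary result. Only the T2 comparison with sham separates them, and the plan gives it no rank among the secondary outcomes, no named contrast, and no rule linking it to a statement about long-term effect. Quality of life, one of the three domains in the aim, has no primary endpoint at all.

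**Working it through.** **1. Which visits can answer which question**

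| Visit | Real vs sham still compared? | Role in End Points | Named for the ANOVA? |
|---|---|---|---|
| T1 (2 weeks) | yes | primary (ICARS, SARA, CCAS); also secondary | no |
| T2 (3 months) | yes | secondary only | yes |
| T3–T5 (open phase) | no: one real course vs two | secondary only (the 6- and 9-month times appear to be T4 and T5) | yes |

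T2 is the only row that is both later than the primary visit and sham-controlled. The ANOVA sentence groups it with three visits that are not sham-controlled. A group-by-time test over T2–T5 mixes the loss or persistence of a first-course effect with the sham arm's response to its own first real course, so it does not isolate persistence against sham.

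**2. Reproducing the plan's sample size**

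Inputs from the Statistical Plan: partial η² = 0.037, f(V) = 0.195, alpha 0.05, power 0.80, N = 54. Check: √(0.037/0.963) = 0.196, against 0.195 stated.

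Model: repeated-measures ANOVA, group-by-time interaction, k = 2 groups, λ = f²·N·m/(1−ρ), df = (m−1) and (N−k)(m−1). The plan gives neither the number of measurements m nor the correlation ρ. Assume m = 2 and ρ = 0.5.

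- N = 54: λ = 0.038025 × 54 × 2/0.5 = 8.21, power 0.803. This is the smallest even N reaching 0.80, so the stated 54 is reproduced.
- N = 60: λ = 9.13, power 0.844.
- N = 40 (the figure in Study Design): λ = 6.08, power 0.671.

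The match is not unique: m = 3 with ρ = 0.4 also gives 54. It therefore does not show which visit the trial was sized for.

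**3. What persistence does to each comparison**

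In change-score terms this model is a difference d = 4f = 0.78 SD, with λ = N·d²/4. Let r be the share of the 2-week effect remaining at T2. The documents give no value, so a range is shown. The SD of change is assumed the same at both visits. At T1, λ does not involve r. At T2, λ = N·(r·d)²/4; for example r = 0.5, N = 60 gives 60 × 0.39²/4 = 2.28.

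| r | T2 power, N = 40 | N = 54 | N = 60 | N for 0.80 at T2 |
|---|---|---|---|---|
| 1.00 | 0.67 | 0.80 | 0.84 | 54 |
| 0.75 | 0.44 | 0.56 | 0.61 | 94 |
| 0.50 | 0.23 | 0.29 | 0.32 | 210 |
| 0.25 | 0.09 | 0.11 | 0.12 | 828 |

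Power at 2 weeks stays at the r = 1.00 row for every r, including r = 0.

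**4. The gate in front of T2**

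A T2 test can follow the primary result only if that result is defined. Three primaries at 0.05 with no combination rule would give a family-wise error of 1 − 0.95³ = 0.143 if any one sufficed and the three were independent (an assumption; related scales would give less). The rule for the three must therefore come first.

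**The case against.** An early primary endpoint with later secondaries on the same scales is a recognised design. The T2 data are collected, randomized, sham-controlled and prespecified. The Statistical Plan names T2 for its ANOVA, so T2 is not ignored. The hypothesis under Ethical Considerations mentions no duration, and the 2-week ICARS and SARA endpoints fit it. All of this stands, and it is why the 2-week primaries should be kept. It does not supply a T0–T2 contrast or say what supports a long-term conclusion.

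A reader might go further and infer that the plan allows the trial to be declared a success on long-term benefit from the 2-week result, or that such a claim is intended. The documents do not support that: they contain no success criterion and no conclusion rule, and they nowhere say how a 2-week result will be reported. A reader might also infer that the trial cannot address persistence at all. That is wrong too, since T2 can, up to 3 months.

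The timing of the primary visit is itself unsettled between Procedures and Study Design. On either reading it falls well before T2, so the point does not depend on which is meant.

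**Conclusion.** The point holds as a mismatch between aim, primary endpoints and stated analysis, and should be corrected. A positive 2-week result would establish a short-term effect only. The sole sham-controlled evidence on persistence is the T0–T2 comparison, which the plan collects but does not single out. The ANOVA as worded also leaves the primary visit without a stated analysis. No treatment estimate is biased by this; the risk lies in what may be concluded.

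The finding on timing rests on the text alone. The power figures rest on m = 2, ρ = 0.5, equal variability at both visits and assumed retention shares. They illustrate that T2 may be underpowered if the effect fades: 0.61 at 75% and 0.32 at 50% retention with 60 subjects, and less with the 40 given in Study Design.

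**What to change.** 1. Keep the 2-week primary endpoints and add T1 to the analysis in the Statistical Plan.
2. State how ICARS, SARA and CCAS are combined at 2 weeks: all must pass, a fixed order, or an adjustment such as Holm.
3. Name the real-versus-sham difference in change from T0 to T2, estimated from a model restricted to T0–T2, as the key secondary for the long-term aim on ICARS, SARA and CCAS. Add SF36 at T2, or remove quality of life from the long-term aim. Test these outcomes in a stated order after the gate in item 2.
4. State the conclusion rule: a long-term effect is claimed only from the T0–T2 comparison, and a 2-week result alone is reported as short-term. T3–T5 are descriptive for efficacy against sham.
5. Reword the objective as short-term effect and its persistence to 3 months.
6. Reconcile Procedures and Study Design on when the first post-treatment visit falls.
7. State the expected power at T2 with its retention assumption.

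Cost: an amendment to wording and analysis, with no new visits or data. The sponsor gives up any long-term claim from the 2-week result alone and accepts that T2 has less power than the 2-week comparison if the effect fades.

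### The protocol gives 40 patients in the design section but needs 54 and proposes 60 in the statistical plan; at 40 the stated 80% power does not hold

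*Combined protocol and SAP*

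**What the plan says.** All the figures stand in the current text of the combined protocol and SAP.

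- **STUDY DESIGN:** the trial is randomised with allocation "anodic tDCS: placebo tDCS = 1: 1" and is described as "cerebellar tDCS 5 days a week for 2 consecutive weeks in 40 patients with neurodegenerative ataxia". The text on block randomisation gives its purpose as "guaranteeing a similar number of patients enrolled in the two groups, even if the trial should be interrupted early".
- **STATISTICAL PLAN (power analysis):** starting from a partial eta-squared of 0.037, an effect size f(V) of 0.195, alpha 0.05 and power 0.80, the plan concludes that "the expected sample size is 54 subjects using a repeated measures ANOVA study". It continues: "The proposed sample size of 60 subjects should be adequate to achieve the main objective of the study".

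The plan does not state how many measurements per patient or what within-patient correlation were used to obtain 54. It gives no dropout rate.

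**The concern.** The design section gives 40 as the total for a two-arm trial. It does not present it as a per-arm number, an interim count, an evaluable set or a subgroup. The statistical plan gives 60 as the proposed size and does not present it as 40 plus an allowance. Both cannot be the enrolment target.

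Two things are at stake. First, if 40 governs, the plan's only statement that its size is adequate is untrue for the trial it describes. Second, whichever number is meant, the protocol does not fix when recruitment is complete. A stop at 40 is full enrolment under the design section, but a stop at two thirds of target (40/60) under the statistical plan. It could later be presented either way.

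**Working it through.** **Step 1: set the totals side by side.** Design section: 40. Statistical plan: 54 required, 60 proposed. The differences are 54 − 40 = 14 and 60 − 40 = 20. The step from 54 to 60 would fit a 10% loss (60 × 0.9 = 54), but that is an inference. Dropout cannot explain 40, which is already below the 54 required.

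**Step 2: what follows without any assumption.** If 54 is the number needed for 80% power, 40 patients under the same inputs give less than 80%. Only the size of the shortfall needs a model.

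**Step 3: reproduce the 54.** Inputs from the STATISTICAL PLAN: f = 0.195 and alpha = 0.05. As a check, √(0.037/0.963) = 0.196, which agrees with 0.195 within rounding. From STUDY DESIGN: two groups, 1:1.

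Assumed, because not stated: the test is the group-by-time interaction, with sphericity, m = 2 measures (the primary outcomes run from baseline to 2 weeks) and correlation ρ = 0.5.

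Formula: noncentral F with λ = f²·N·m/(1 − ρ), df1 = m − 1, df2 = (N − 2)(m − 1). With m = 2 and ρ = 0.5, λ = 0.195² × N × 2/0.5 = 0.1521 × N.

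| N | λ | df | Power |
|---|---|---|---|
| 40 | 6.08 | 1, 38 | 0.671 |
| 52 | 7.91 | 1, 50 | 0.788 |
| 54 | 8.21 | 1, 52 | 0.803 |
| 60 | 9.13 | 1, 58 | 0.844 |

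So 54 is the smallest even total reaching 80%, as the plan says.

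Cross-check on the change score: with ρ = 0.5 the standard deviation (SD) of the change equals the SD of a single score, and the group difference in change is 4f = 0.78 SD. The normal approximation gives 26 per arm (52 in total), with power 0.69 at 20 per arm and 0.86 at 30 per arm.

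**Step 4: effect detectable at 40.** Solving the same model for 80% power at N = 40 gives f = 0.227. That is a partial eta-squared of 0.227²/(1 + 0.227²) = 0.049, against the planned 0.037.

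**Step 5: vary the unstated inputs.** For each m, the table gives the non-negative correlations for which 54 is the smallest even N reaching 80%.

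| m | ρ | Power at 40 | Power at 60 |
|---|---|---|---|
| 2 | 0.497–0.515 | 0.67–0.68 | 0.84–0.85 |
| 3 | 0.379–0.402 | 0.66–0.68 | 0.84–0.86 |
| 4 | 0.266–0.293 | 0.65–0.67 | 0.85–0.86 |
| 5 | 0.160–0.191 | 0.65–0.67 | 0.85–0.86 |
| 6 | 0.060–0.095 | 0.65–0.67 | 0.85–0.86 |

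Across all of these, the f detectable with 80% power at N = 40 is 0.223 to 0.228.

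**The case against.** **The 60 is better supported.** Only the statistical plan labels a number as the sample size, and it gives a derivation. The 40 appears once, without justification, in a sentence about design and blinding. It may be a single wrong number, in which case the power claim stands. That is a fair reading, and it is why the power consequence is stated conditionally. But the documents do not settle it, and the contradiction remains on either reading.

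**The range at 40 is narrow by construction.** It keeps only settings that return 54. In the same model with ρ = 0.5, power at 40 is 0.67 for 2 measures but 0.83 for 4 and 0.92 for 6; with 2 measures and ρ = 0.7 it is 0.87. This stands as a limit on the magnitude: 0.65 to 0.68 is what the plan's own 54 implies, not an independent estimate of the trial's power. The more favourable settings do not rescue the text, because they contradict the 54 (6 measures with ρ = 0.5 would need only 29). In the other direction, scaling λ as f²·N·(m − 1) does not return 54 for 2 to 6 measures and gives power at 40 of only about 0.22 to 0.53. The derivation of the 54 is not challenged here.

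**Two measures is one choice.** The mixed-model ANOVA in the statistical plan refers to T2 to T5, and with 5 or 6 measures the 54 requires correlations of only 0.06 to 0.19, arguably low for repeated scores in the same patients. So 67% is illustrative and should not be copied into the protocol unless its inputs are confirmed.

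**The early-interruption phrase is not a stopping rule.** Agreed. It explains the use of blocks, which serve that purpose at either total. It matters here only because full and early recruitment cannot be told apart without a single target.

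**Conclusion.** The concern holds: the enrolment number is wrong as written in one of the two sections. That 40 patients fall short of 80% power follows directly from the plan's own 54 and needs no outside input.

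The size of the shortfall is conditional on 40 being the operative number, on the plan's 54 being taken as given, and on assumed values for the number of measures and the correlation. On that basis power is 0.65 to 0.68 instead of 0.80, about 12 to 15 percentage points lower. If 60 is operative, power in the same settings is 0.84 to 0.86, the adequacy sentence is consistent with the plan's calculation, and the defect is the 40 in the design section.

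**What to change.** State one enrolment target, identically, in STUDY DESIGN and STATISTICAL PLAN, together with the number of measures and the correlation used to obtain 54.

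- **If the target is 60:** correct the 40 in STUDY DESIGN.
- **If the target is 40:** delete the sentence "The proposed sample size of 60 subjects should be adequate to achieve the main objective of the study". Restate, from the stated inputs, either the power at 40 or the effect detectable with 80% power. If the inputs are 2 measures and correlation 0.5, these are about 67% and f about 0.227.

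The cost is a short text amendment. With 40 as the target, the stated power becomes less favourable, but no extra patients are needed to correct the figure. With 60 as the target, the trial needs 20 more patients than the design section describes, which matters only if recruitment was planned on that section.

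### Allocation is stratified by pathology and the primary scales are measured at baseline, but the efficacy model names neither; adding both costs no patients or visits and can gain precision

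*Combined protocol and SAP*

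**What the plan says.** STUDY DESIGN sets 1:1 allocation and says "A randomized stratification by type of pathology will be implemented", followed by blocked randomisation. The stated purpose is to balance each pathology between real and sham. Four diagnoses are eligible: spinocerebellar ataxia, Friedreich's ataxia, "multisystem atrophy, sporadic ataxia in adult onset will be included". The strata themselves are not enumerated. The clinical evaluation takes place "at baseline (T0), after 2 weeks of treatment with tDCS (T1") and again at 3 months (T2). An open phase follows in which all patients receive real stimulation (T3 to T5).

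END POINTS gives three primary outcomes (ICARS, SARA, CCAS), each a change over the first two weeks, for example "Change in the Scale for the Assessment and Rating of Ataxia (SARA) Score (Baseline – 2 Weeks").

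STATISTICAL PLAN gives the efficacy analysis in one sentence: "at T 2-3-4-5 we will use a mixed-model ANOVA". It lists no factor, covariate or stratum, and neither T0 nor T1 is among the visits. The only baseline analysis is t tests on age and education. For sample size, the plan says "the expected sample size is 54 subjects using a repeated measures ANOVA study" and proposes 60, whereas STUDY DESIGN says 40.

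**The concern.** Pathology was judged important enough to stratify on. If it predicts the two-week change, balancing it between arms makes the treatment difference less variable, but an analysis without the stratum still counts the between-pathology variation as error. The standard error is then too large and the test conservative. Likewise, a change score fixes the coefficient of the baseline at 1, whereas fitting the baseline as a covariate lets the data set it, which is more precise unless rho is very high.

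With 40 or 60 patients, precision at T1 limits what the trial can show. The T1 model also has still to be written, since T1 is missing from the plan's list. If its terms are left open, the covariates could be chosen after unblinding.

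**Working it through.** **Inputs from the STATISTICAL PLAN.** Partial eta squared 0.037, f = 0.195 (check: sqrt(0.037/0.963) = 0.196), alpha 0.05, power 0.80, N = 54. STUDY DESIGN gives N = 40 and the plan proposes 60.

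**Step 1: reproduce the plan's 54.** For a two-group, two-visit group-by-time test, the noncentrality is lambda = f² × N × 2/(1 − rho), on 1 and N − 2 df. With rho = 0.5:

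- N = 54: lambda = 0.038025 × 54 × 4 = 8.21, power 0.803
- N = 40: lambda = 6.08, power 0.671
- N = 60: lambda = 9.13, power 0.844

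So 54 is reproduced. Two visits and rho 0.5 are not stated in the plan, and they are not the only route: a between-group test with four visits and rho 0 gives the same lambda (0.038025 × 54 × 4 = 8.21). For a two-arm change score, lambda = d² × N/4, so d = 4 × 0.195 = 0.78 SD of the change. That effect is held fixed below.

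**Step 2: what the two terms do to the variance.** With equal SDs at T0 and T1, the variance of the treatment effect relative to the change score is

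(1 + rho)/2 × (1 − R2),

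with a small-sample factor of 1 + 1/(N − 6) and error df of N − 6 (four strata assumed, so three df, plus one for baseline). R2 refers to the *change*: stable differences in level between pathologies cancel in a change score and bring no gain.

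Example, N = 40, rho 0.8, R2 = 0: lambda = 6.084/0.90/(1 + 1/34) = 6.57, power 0.702.

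**Step 3: simulation.** 200,000 trials per cell, four strata balanced by arm, bivariate normal T0 and T1. Power of the change-score t test against the model of T1 on treatment, T0 score and stratum:

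| N | R2 | Change score | rho 0.5 | rho 0.8 | rho 0.9 | rho 0.95 | rho 0.98 |
|---|---|---|---|---|---|---|---|
| 40 | 0 | 67% | 78% | 70% | 68% | 67% | 66% |
| 40 | 10% | 68% | 82% | 75% | 72% | 71% | 71% |
| 40 | 20% | 68% | 86% | 80% | 77% | 76% | 76% |
| 60 | 0 | 84% | 92% | 87% | 85% | 85% | 84% |
| 60 | 10% | 85% | 95% | 90% | 89% | 88% | 87% |

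The simulated 0.701 at N = 40, rho 0.8, R2 = 0 agrees with the formula's 0.702.

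The introduction describes the spinocerebellar ataxias as "characterized by slowly progressive ataxia of walking, posture and limbs". That gives no support for a two-week correlation as low as 0.5, so the rho 0.5 column is shown only because it reproduces the plan's 54.

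**Step 4: break-even.** With R2 = 0 the two analyses have equal power at rho of about 0.93 (N = 40) or 0.955 (N = 60). Above that the full model loses slightly: at N = 40, 0.4 points at rho 0.95 and about 1.1 at rho 0.98. An R2 of 1–2% (rho 0.95) or about 3% (rho 0.98) restores parity. Expressed as patients, the change-score N matching 40 under the full model with R2 = 0 is 51, 43, 40.5, 40 and 39 across the five values of rho.

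**Step 5: type I error, N = 40.** At R2 of 0, 10% and 20%, the change score without stratum gives 5.1%, 3.8% and 2.8%. The full model gives 4.9–5.1%.

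**Step 6: sensitivity, N = 40.** Unequal strata (16/12/8/4) change the results by at most 0.4 points. With R2 = 0 and a T1 SD 10–20% larger than the T0 SD at rho 0.8–0.9, the lowest power is 0.657 against 0.67, a loss of about 1.5 points. With a T1 SD 10% smaller, the full model reaches 0.75–0.82.

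**The case against.** The baseline is not ignored. The primary outcomes are change scores, and a mixed ANOVA with T0 as a time level would use it too. What remains is a choice between a covariate and a change score, and at the high correlations plausible over two weeks the baseline term is worth almost nothing (67% against 68%, 67% and 66% at rho 0.9, 0.95 and 0.98, with R2 = 0 and N = 40). That stands, and it is why the comparator here is the change score and not the T1 score alone.

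The pathology gain rests on R2, and nothing in the documents indicates that two-week change differs by diagnosis. That also stands: 10% and 20% are assumptions.

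The power figures depend on holding the effect at 0.78 SD of the change. If f = 0.195 is held fixed instead, lambda at N = 40 and rho 0.8 is 0.038025 × 40 × 2/0.2 = 15.21, with change-score power 0.967, and at rho 0.9 it is 0.9997. There would be little power left to gain. This is correct, and the percentages therefore illustrate a scenario. The effect on interval width does not depend on the assumed effect: apart from the small-sample factor, the standard error falls by a factor of sqrt(0.9) = 0.95 at rho 0.8, and by the same factor for an R2 of 10%.

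Finally, the plan's sentence lists no terms at all, so the omission may be brevity and not a decision. Either way the terms are not fixed in advance.

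**Conclusion.** The concern holds, as a matter of precision. The plan stratifies on pathology and measures each primary scale at T0, yet names neither in its only efficacy model, and it states no model for T1. A change-score analysis would be unbiased, and leaving out the stratum makes it at most conservative.

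At N = 40 the benefit ranges from slightly negative (about 1 point of power lost at rho 0.98 with uninformative pathology; about 1.5 in the worst unequal-SD case tried) to 7 points at rho 0.8 with R2 10%, and 12 points (80% against 68%) with R2 20%. These figures assume an effect of 0.78 SD of the change, four strata and, except where stated, equal SDs at T0 and T1. Neither rho nor R2 is in the documents. Confidence that there is a useful gain is medium. The change should be made because the possible loss is small, the possible gain is several times larger, and fixing the terms removes a choice that could otherwise be made after unblinding.

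**What to change.** For each primary scale, pre-specify a linear model of the T1 score with treatment, the T0 score of that scale and pathology stratum as fixed effects. A repeated-measures model on T1 and T2, the two blinded follow-ups, with the same terms and treatment-by-visit would also serve. List the strata, and set a rule for merging sparse ones, in advance and blind to arm and outcome. Report the adjusted real-minus-sham difference at T1 with its 95% confidence interval.

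The cost is SAP wording only, with no extra patients or visits. The model spends up to four degrees of freedom: three for four strata and one for baseline. The two stated sample sizes, 40 and 60, need reconciling separately; the recommendation is the same for either.
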